6.3.2.5 Adverse Event Assessment

6.4 Post-Treatment Surveillance (Follow-Up)

6.4.1 After completion of adjuvant chemotherapy, subjects will undergo follow-up, every 3 months, +/- 14 days, for a total of 36 months from the date of surgery.

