6.4.1.5 Survival Status

6.4.1.6 Recurrence of disease (date of recurrence)

6.4.1.7 Adverse Event Assessment (per Section 13.6.3)

6.4.2 Patients will undergo imaging for residual or recurring tumor with either CT (chest with contrast and abdomen/pelvis with and without contrast) or CT/PET (skull base to mid-thigh). The interval of this imaging can be every 3-6 months, at the discretion of the treating investigator.

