8.0 CRITERIA FOR STUDY CONTINUATION OR DISCONTINUATION

All patients who are enrolled on the study and begin any of their intended post-operative adjuvant therapy will be counted as evaluable for the study. This inclusion will be regardless of how much of the postoperative treatment they ultimately receive.

Criteria for discontinuation of post-operative treatment will be:

- a) Unacceptable toxicity
- b) Treatment delay due to toxicity > 2 weeks.
- c) Treatment delay for any other reason > 3 weeks.

Patients who discontinue treatment for these reasons will remain on protocol and will move on to surveillance/follow-up for disease recurrence

Disease recurrence, will be defined as radiographic tumor evidence detected by surveillance imaging. Confirmation of recurrence by biopsy will be at the discretion of the treating physician.

If a subject has disease recurrence during surveillance / follow-up, then further study follow-up can be discontinued; the subject will come off-study, and can be followed per standard clinical care at the investigator's discretion.

The patient may withdraw from the study at any time for any reason. Similarly, an investigator may remove a patient from the study for non-compliance with study protocol at any time. Patients removed from the study for these reasons will be replaced.

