15.0 APPENDIX I: SCHEDULE AND FLOW OF EVALUATIONS

15.1 ARM 1: Node-Negative, Adjuvant Chemotherapy.

Study Procedures	Screening & Baseline (1)	Arm 1: Cycle 1 (6)	Arm 1: Cycle 2 (6)	Arm 1: Cycle 3 (6)	Post-Treatment Surveillance, every 3 months (7)
Informed Consent	X				
History & Physical Exam; Vitals (2); ECOG PS	X	X	X	X	X
CBC + differential + platelets	X	X	X	X	X
CMP: Serum Chemistries (3)	X	X	X	X	X
AE Assessment		X	X	X	X
Pregnancy Test	X				
Tumor for genetic profile (4)	X				
Imaging (5)	X				X
Chemo, Adjuvant		X	X	X	
Survival Status, Recurrence					X

1. Screening procedures must be obtained within 28 days registration, with the exception of radiographic studies and tumor samples for baseline profiles.
2. Vital signs includes blood pressure, respiratory rate, height, and weight.
3. Serum chemistries to include: liver enzymes (AST, ALT, alkaline phosphatase), blood urea nitrogen (BUN), creatinine, electrolytes (sodium, potassium, chloride, calcium, bicarbonate), total protein, albumin, total bilirubin, glucose.
4. Tumor samples from diagnostic biopsy (before neo-adjuvant chemo) and surgery (after neo-adjuvant chemo) should be obtained (after subject consents to participate).
5. Can be either (1) CT of the chest with contrast and CT of the abdomen/pelvis with and without contrast, or (2) PET/CT from the skull base to mid-thigh. Baseline imaging must be after surgery, and within 42 days of starting adjuvant chemotherapy.
6. Procedures are to be repeated at the beginning of each cycle and can be assessed up to 2 days in advance of D1 for each cycle. These cycles are 14 days long if FOLFOX used and 21 days long if CAPEOX used.
7. Three month interval begins from the end of completion of chemotherapy, and continues until 36 months after surgery (unless patient comes off study, per Section 6). These assessments can be +/- 14 days from planned date. Imaging assessments during follow-up can occur every 3-6 months, per investigator's standard practice. If subject has disease recurrence, follow-up will stop.

15.2 ARM 2: Node-Positive, Adjuvant Chemoradiation.

Study Procedures	Screening & Baseline (1)	Arm 2: Chemo alone, Cycle 1 28-day cycle (6)	Arm 2: ChemoRT, 5 weeks Schedule is for each week					Arm 2: Chemo alone, Cycle 2 28-day cycle (6)	Arm 2: Chemo alone, Cycle 3 28-day cycle (6)	Post-Treatment Surveillance, every 3 months (7)
			W 1	W 2	W 3	W 4	W 5			
Informed Consent	X									
History & Physical Exam; Vitals (2); ECOG PS	X	X	X	X	X	X	X	X	X	

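### The recurrence definition admits only radiographic findings on post-treatment surveillance imaging, while the endpoint covers the whole time on trial; some recurrences would be counted late or lost.

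*Combined protocol and SAP*

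**What the plan says.** Section 8.0 defines the event: "Disease recurrence, will be defined as radiographic tumor evidence detected by surveillance imaging". It adds: "Confirmation of recurrence by biopsy will be at the discretion of the treating physician". Biopsy is therefore optional confirmation and not a separate way to establish recurrence.

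Section 6.4, on post-treatment surveillance, fixes when surveillance happens: "After completion of adjuvant chemotherapy, subjects will undergo follow-up, every 3 months, +/- 14 days, for a total of 36 months from the date of surgery". On scans, Section 6.4.2 says: "The interval of this imaging can be every 3-6 months, at the discretion of the treating investigator". Footnote 7 of Appendix I reads: "Three month interval begins from the end of completion of chemotherapy, and continues until 36 months after surgery". Sections 6.2 and 6.3 list the on-treatment evaluations for the two arms, and imaging is not among them. The last protocol scan before treatment is the baseline one (Appendix I, footnote 5): "Baseline imaging must be after surgery, and within 42 days of starting adjuvant chemotherapy".

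Two other places are wider than Section 8.0. Section 2.4 makes the secondary endpoint the recurrence rate over the time on trial, by arm and against historical controls. Item 6.4.1.6 collects recurrence and its date at follow-up visits, separately from imaging and with no limit on how it was found. Section 10.0 names time to recurrence and recurrence free survival as secondary outcomes but does not define their events, start date or censoring.

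**The concern.** The definition sets two conditions: the evidence must be radiographic, and it must come from surveillance imaging. In this protocol surveillance is a phase that begins when adjuvant treatment ends. The endpoint window therefore includes a treatment period in which, on the literal wording, no recurrence can be established. Findings made outside imaging do not qualify at any time.

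Section 10.0 has no event definition of its own, so an analyst has only Section 8.0 to apply. One analyst could follow it literally; another could follow Section 2.4 and item 6.4.1.6. They could count the same patient differently or give the event a different date. The literal rule errs in one direction: late dating lengthens time to recurrence, and lost events lower the recurrence rate. Adjuvant treatment is longer in Arm 2, the node-positive group whose outcome Section 3.1 expects to be poorer, so the late dating is greater there.

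**Working it through.** The plan states no figure on this point, so there is nothing to reproduce. The check has two parts.

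**1. Which findings meet the Section 8.0 wording?**

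| First documentation | Radiographic? | Surveillance imaging? | Result on a literal reading |
|---|---|---|---|
| Scheduled scan after treatment | yes | yes | counted |
| Symptom-prompted scan during treatment | yes | no | not counted at that date |
| Unscheduled scan during follow-up | yes | unclear, term not defined | open to dispute |
| Endoscopy, cytology or biopsy alone | no | no | not counted at that date |

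A case in rows 2 to 4 that is not accepted at first documentation becomes an event, with a later date, if a subsequent surveillance scan shows the tumour. It is lost if the patient dies, withdraws or is removed before such a scan. Section 8.0 has patients who withdraw, or who are removed for non-compliance, replaced. It does not say whether a recurrence already found in such a patient still counts.

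**2. When does the first surveillance scan fall?**

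Inputs:
- Arm 1: three cycles of 14 days (FOLFOX) or 21 days (CAPEOX), from Section 7.1 and Appendix I, footnote 6.
- Arm 2: one 28-day cycle, 5 weeks of chemoradiation, then two 28-day cycles, from Sections 7.2 and 7.3.
- First surveillance scan 3 to 6 months after the end of treatment, taken as 91 to 182 days. This is inferred from Section 6.4.2 and footnote 7; neither fixes a date for the first scan.
- Treatment completed without delay.

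Formula: days from treatment start to first scan = treatment length + 91 (or 182).

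| Regimen | Treatment length | At 3 months | At 6 months |
|---|---|---|---|
| Arm 1, FOLFOX | 3 × 14 = 42 | 42 + 91 = 133 | 42 + 182 = 224 |
| Arm 1, CAPEOX | 3 × 21 = 63 | 63 + 91 = 154 | 63 + 182 = 245 |
| Arm 2 | 28 + 35 + 2 × 28 = 119 | 119 + 91 = 210 | 119 + 182 = 301 |

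At the same scan interval, Arm 2 is later by 119 − 63 = 56 days (against CAPEOX) to 119 − 42 = 77 days (against FOLFOX).

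The baseline scan may precede treatment by up to 42 days. The longest gap between two protocol scans on these assumptions is then 224 + 42 = 266 days (FOLFOX), 245 + 42 = 287 days (CAPEOX) or 301 + 42 = 343 days (Arm 2).

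**The case against.** The strongest reply is that nothing in the protocol says on-treatment or otherwise detected recurrences are to be discarded. Section 2.4 and item 6.4.1.6 both point to a wider count. A reader might infer from Section 8.0 that such recurrences are simply left out of the endpoint; the documents do not support that. They are inconsistent with one another rather than clearly exclusive. A tumour that recurs during treatment would also usually still be visible on the first surveillance scan, and follow-up runs to 36 months from surgery. Late counting is the usual consequence and loss the less common one. Both points stand.

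The timing figures are conditional too. Imaging frequency is discretionary, and patients who stop treatment early move to surveillance sooner, so their interval is shorter. A radiographic rule also has merit, because it is objective and fairly uniform. Finally, recurrence is a descriptive secondary outcome in a non-randomised pilot of 40 patients, with historical controls as the stated comparator. All of this limits the weight of the point.

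It does not remove it. Section 8.0 is the only event definition in the document, and as worded it does not admit a biopsy-proven recurrence found at endoscopy or one seen on a scan prompted by symptoms during treatment.

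**Conclusion.** The concern holds as a mismatch between the event definition and the endpoint it serves. Followed literally, Section 8.0 would date some recurrences late and lose a smaller number.

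The part that can be sized is the timing: a first surveillance scan at 133-224, 154-245 or 210-301 days after treatment start for FOLFOX, CAPEOX and Arm 2, and a delay 56-77 days longer in Arm 2. This rests on completed treatment, no delays, and a first scan 3-6 months after treatment ends.

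The number of events lost cannot be sized. The documents give neither a recurrence rate nor the share of recurrences first found outside surveillance imaging, so any figure for missing events would be conjecture. Two further inferences also go beyond the text. The first is that the historical controls count recurrences more broadly: the protocol names no control series for recurrence and gives no definition for one, so the most that can be said is that comparability is not established. The second is that this endpoint is meant to drive a later trial: Section 2.3 gives that role to the primary feasibility endpoint, which is unaffected.

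The definition should be corrected, but the point does not threaten the main conclusion of the pilot.

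**What to change.** Replace the definition in Section 8.0 and carry it into Section 10.0:

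- Recurrence is the first documentation by any imaging, scheduled or unscheduled, or by histology or cytology (including endoscopic biopsy), at any time from registration and including the treatment period.
- The date and the method of first documentation are recorded.
- For recurrence free survival, death without documented recurrence is an event.
- A sensitivity analysis limits recurrence to surveillance imaging.

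The cost is a few sentences of protocol text and one case report form field for method of detection. No scans are added and treatment is unchanged. The downside is somewhat less uniform ascertainment; the recorded method and the sensitivity analysis let a reader judge its effect.

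The new definition does not remove the difference in scheduled scan timing between the arms. That should be stated wherever time to recurrence is reported by arm.

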9.0 CORRELATIVE / SPECIAL STUDIES

Tumor samples obtained at diagnosis and from the surgical specimen will be referred for genetic profiles. These profiles are being developed in collaboration with the cancer genomics division in the department of molecular and human genetics at Baylor College of Medicine.

These profiles will assess alterations in gene expression consistent with the CGAR gastric cancer subtypes, correlating these to the nodal responses observed in the treated patients. Within these proposed subtypes of gastric cancer, it is reasonable to consider that different subtypes respond or evolve in different ways when treated with this standard chemotherapy. Being able to correlate these responses to the clinical outcomes at time of surgery (i.e.: the presence or absence of nodal disease) could be developed in future studies in a predictive manner. Thus, this will serve as an exploratory gene analysis, both for static gene expression at time of diagnosis as well as evolution of gene expression in response to chemotherapy, which could in turn be developed in future studies as a predictor of chemotherapy response. Tumor samples will remain in pathology archive and will be batch-sent for analysis.

Samples will not be banked after research. Any remaining samples will be discarded.

10.0 STATISTICAL CONSIDERATIONS

The primary objective is to determine the feasibility of patients enrolling and receiving either postoperative chemoradiation or chemotherapy alone, based upon nodal status. Based on our experience, we projected that the eligible patients would receive chemoradiation or chemotherapy alone in 3:1 ratio after surgery. We designed this pilot study on 30 patients who receive chemoradiation and on 10 patients who receive chemotherapy alone based upon nodal status at surgery, for a total of 40 patients. At 50% of complete rate, the confidence intervals will have widths of a most +/- 17% and +/- 26.5% (confidence intervals calculated using Wilson method). For control purposes, no more than 30% of patients with node negative disease should be unable to receive postoperative chemotherapy. In order for postoperative chemoradiation to be a feasible recommendation in patients who have lymph node positive disease at time of surgery after preoperative chemotherapy, a majority of patients must be able to receive this chemoradiation in its entirety.

The primary endpoint is the proportion of patients who complete the recommended therapies as indicated by their surgical nodal status. The primary endpoint will be evaluated when the last patient completes the postoperative chemotherapy or chemoradiation assigned. Descriptive and summary statistics will be computed for demographics and clinical data of all patients enrolled in the study. In each group, complete rates will be summarized with a point estimate and 95% confidence interval (Wilson method). If no more than 30% of patients are unable to complete all protocol therapy, then this will be considered a feasible treatment for these patients.

Time to recurrence and recurrence free survival are secondary outcomes. These will be summarized using survival analysis methods, such as Kaplan-Meier survival curves, median survival time and 97% confidence interval. For the correlative study, tumor samples obtained at diagnosis and from the surgical specimen to see the changes in gene expression, categorized based upon correlation to nodal status. A paired t-test and multiple comparisons will be performed. Analysis of tumor genetic profile should be almost universally assessable from tumor samples acquired. No special preparation is necessary for these samples. Expect that no more than 10% of patients will be unable to have tumor profiles assessed on both pre- and post- chemotherapy tumor specimens.

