2.0 SYNOPSIS

2.1 Primary Objective:

To determine the feasibility of patients enrolling and receiving either postoperative chemoradiation or chemotherapy alone, based upon nodal status at surgery, following preoperative chemotherapy.

2.2 Secondary Objectives:

To evaluate the rate of cancer recurrence in patients assigned to treatment based upon node status

To explore the potential correlation between changes in expression of a pre-specified panel of genes identified as relevant to gastrointestinal cancers in response to preoperative chemotherapy, using presence of nodal involvement at time of surgery as an indicator of response.

2.3 Primary Endpoint:

The proportion of patients who would meet the criteria would be estimated to demonstrated successful enrollment and treatment of therapies including postoperative chemotherapy or chemoradiation as indicated by the nodal features, which would justify development of a study powered to demonstrate survival benefit to patients using this approach. Expect that no more than 30% of patients will be unable to complete all protocol therapy.

2.4 Secondary Endpoints:

The recurrence rate while on trial will be reported for the two arms of the trial, and compared to historical controls

Observation of changes in gene expression as a response to chemotherapy, categorized based upon correlation to nodal status. Expect that no more than 10% of tumors will be unable to have tumor assessed on both pre- and post- chemotherapy tumor specimens.

2.5 Study Design:

Open-label, stratified, two arm design. All patients receive same initial standard preoperative chemotherapy and surgical resection. Patients will then be assigned to either standard postoperative chemotherapy if node negative at surgery or standard postoperative chemoradiation if node positive at surgery.

2.6 Number of Patients:

Forty patients.

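### Kaplan-Meier is the only method named for time to recurrence and deaths without recurrence have no stated handling; a cumulative incidence estimate would fit the endpoint better

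*Combined protocol and SAP*

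**What the plan says.** Section 10.0 lists two time-to-event outcomes: "Time to recurrence and recurrence free survival are secondary outcomes". The method follows for both at once: "These will be summarized using survival analysis methods, such as Kaplan-Meier survival curves". The section defines neither outcome. It gives no time origin, no censoring rule and no handling of death before recurrence. Competing risks and cumulative incidence are not mentioned anywhere.

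Section 8.0 supplies the event: "Disease recurrence, will be defined as radiographic tumor evidence detected by surveillance imaging". Death is not part of it. The same section adds: "If a subject has disease recurrence during surveillance / follow-up, then further study follow-up can be discontinued".

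Section 6.4.1 sets follow-up visits "every 3 months, +/- 14 days, for a total of 36 months from the date of surgery". Item "6.4.1.5 Survival Status" is collected at each visit, as is the date of recurrence (6.4.1.6). Section 6.4.2 allows imaging every 3 to 6 months at the investigator's discretion.

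The synopsis (Section 2.4) words the recurrence endpoint differently: "The recurrence rate while on trial will be reported for the two arms of the trial, and compared to historical controls". It names no estimator.

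**The concern.** Kaplan-Meier suits recurrence-free survival if, as is usual, that endpoint counts recurrence or death. Time to recurrence is different. If death counted as an event there too, the two outcomes would coincide and there would be no reason to list both. If death is not an event, a routine Kaplan-Meier analysis censors it. The patient leaves the risk set, and the estimate assumes that this patient would later have recurred at the same rate as those who remain. So 1-KM describes recurrence in a setting where nobody dies first, which is not the share of patients who actually have a recorded recurrence.

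The protocol makes this more than a formality. Study follow-up may end at recurrence, so deaths seen during surveillance will mostly be deaths without recorded recurrence, which is the competing event. Recurrence is also the first secondary objective listed in Section 2.2. A figure that is too high for a known and avoidable reason is worth preventing before the analysis is run.

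**Working it through.** **Inputs from the documents.** There are 30 patients planned on chemoradiation and 10 on chemotherapy alone (Section 10.0), with a 36-month horizon from surgery (Section 6.4.1) and recurrence defined by imaging only (Section 8.0). No recurrence rate and no rate of death without recurrence is given, so both are assumed below.

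**The plan's own figure.** The plan states no precision for time to recurrence. Its only computed figure is the Wilson half-width for the completion rate at 50%, given as at most 17% and 26.5%. With half-width = (z/2)/√(n + z²) and z = 1.96:
- n = 30: 0.98/√33.84 = 16.85%
- n = 10: 0.98/√13.84 = 26.34%

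Both reproduce. They concern the primary endpoint and serve here only to show how little precision these group sizes allow.

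**Direction.** Let h1 be the hazard of recorded recurrence and h2 that of death without it, with cumulative hazards H1 and H2.
- Cumulative incidence = ∫ h1·exp(−H1 − H2)
- 1-KM with deaths censored = ∫ h1·exp(−H1)

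The second is larger whenever h2 is positive before recurrences occur, and the two are equal if h2 = 0.

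**Size, fixing the cumulative incidences.** Let C1 and C2 be the 36-month cumulative incidences of recorded recurrence and of death without it. If h1/h2 is constant over time, H = −ln(1 − C1 − C2) and 1-KM = 1 − exp(−H·C1/(C1 + C2)). Take C1 = 50% (assumed).

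| C2 (assumed) | H | C1/(C1+C2) | 1-KM | Excess, points |
|---|---|---|---|---|
| 0% | 0.693 | 1.000 | 50.0% | 0 |
| 5% | 0.799 | 0.909 | 51.6% | 1.6 |
| 10% | 0.916 | 0.833 | 53.4% | 3.4 |
| 20% | 1.204 | 0.714 | 57.7% | 7.7 |

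**Size, fixing 1-KM instead.** Let R be 1-KM at 36 months and D the net probability of death without recurrence, that is, with recurrence removed. With constant hazards, C1 = [ln(1−R)/(ln(1−R) + ln(1−D))]·[1 − (1−R)(1−D)]. For R = 45% and D = 10%: 0.598/(0.598 + 0.105) × (1 − 0.55 × 0.90) = 0.850 × 0.505 = 42.9%, an excess of 2.1 points. For R of 30%, 45% and 60%:
- D = 5%: excess 0.7, 1.0 and 1.3 points
- D = 10%: excess 1.4, 2.1 and 2.6 points
- D = 20%: excess 2.9, 4.2 and 5.3 points

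Simulating both estimators (4,000 runs per setting) at R = 45% and D = 10% gives an average gap of 2.07 points for n = 30 and 2.09 for n = 10, in agreement with the formula.

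**Against sampling error.** The approximate 95% half-width for a 50% proportion is 1.96·√(0.25/n). That is 17.9 points for n = 30 and 31.0 for n = 10. The largest gap above, 7.7 points, is less than half of the smaller of these.

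**The case against.** Several stronger readings are tempting, and the documents do not support them.

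- **That the plan prescribes censoring of deaths.** It does not say so. Kaplan-Meier is offered as an example of survival methods, and others remain open. Censoring is an inference from the imaging-only definition and the separate listing of recurrence-free survival. The inference is sound, but what the plan itself contains is a gap.

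- **That the comparison with historical controls is biased.** Section 2.4 does not tie its recurrence rate to Kaplan-Meier, and the rate can be read as a simple proportion. With complete follow-up to 36 months, that proportion equals the cumulative incidence and carries no such excess. The estimator used for the controls is not given either.

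- **That 1-KM overstates true recurrence.** It exceeds recorded recurrence. With imaging every 3 to 6 months, some deaths may be recurrences that no scan caught, and for those patients the error runs the other way. In the 10% row, if a fraction f of the deaths were missed recurrences, true recurrence is 50 + 10f points. 1-KM (53.4) is closer to the truth than the cumulative incidence (50) once 10f exceeds half the gap, 1.7 points, so f > 0.17. It is itself too low once 10f > 3.4, so f > 0.34. The documents give no value for f. Cumulative incidence does not repair this.

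It can also be said that time to recurrence with deaths censored is a recognised cause-specific quantity, that recurrence-free survival is already planned, and that the gap is small beside the sampling error. All of this stands, and it sets the severity. It does not justify leaving unstated what a reported recurrence probability means, since the better-suited estimate uses the same data.

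**Conclusion.** The point holds in limited form. Time to recurrence and recurrence-free survival share one named method, neither is defined, and the handling of death without recurrence is missing. The natural execution would censor those deaths, and 1-KM would then exceed the cumulative incidence of recorded recurrence. Over an assumed 5% to 20% of deaths without recorded recurrence by 36 months, the two calculations together put the excess at roughly 1 to 8 points. The upper end needs 20% such deaths, which nothing in the documents supports or excludes. The sizes also rest on a constant ratio of the two hazards.

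Severity is low. The outcome is descriptive, the gap lies within sampling error in both arms, no decision rule depends on it, and neither the primary endpoint nor the sample size is touched.

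**What to change.** In Section 10.0:

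1. Define both endpoints, with time origin, events and censoring rules. Time to recurrence counts recorded radiographic recurrence; recurrence-free survival counts recurrence or death.
2. Estimate time to recurrence by the Aalen-Johansen cumulative incidence function, by arm, with death without recorded recurrence as a competing event. Keep Kaplan-Meier for recurrence-free survival.
3. Report the two side by side, because deaths that hide a missed recurrence are captured only by recurrence-free survival.
4. State whether the recurrence rate in Section 2.4 is a proportion or a time-to-event estimate. If it is the latter, use the same estimator for the trial and for the historical controls.

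The cost is a few sentences of wording. Survival status and date of recurrence are already collected. The date of death is not listed by name in Section 6.4.1, but recurrence-free survival needs it in any case. Standard software suffices, and no visit, scan or patient is added.

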4.3 Genetic profile correlative studies

- 4.3.1 All patients will have undergone two tumor tissue acquisitions during standard clinical practice. Specimens from these acquisitions must be available:
- Prior to initiation of preoperative chemotherapy, tumor tissue will be obtained from the diagnostic biopsy samples;
 - Tumor tissue will be obtained at the time of surgery.

Both of these samples will be a part of standard of care, thus no additional biopsies beyond this standard will be performed for the study.

A preselected panel of genetic markers will be assessed for expression within each sample, and compared for differences, pre- and post-chemotherapy. These differences will be correlated for any response in tumor, i.e., node positive versus node negative.

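### The gene-expression objective asks whether change differs by nodal status, but the only test named, a paired t-test, does not compare node-positive with node-negative patients

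*Combined protocol and SAP*

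**What the plan says.** The nodal contrast appears in every section that describes the correlative work:

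- Section 2.2 (objective): "To explore the potential correlation between changes in expression of a pre-specified panel of genes", with nodal involvement at surgery serving as the marker of response.
- Section 2.4 (endpoint): "Observation of changes in gene expression as a response to chemotherapy, categorized based upon correlation to nodal status".
- Section 4.3 (design): "These differences will be correlated for any response in tumor, i.e., node positive versus node negative".
- Section 9.0: the profiles are assessed by "correlating these to the nodal responses observed in the treated patients". The section calls the analysis exploratory and widens it to "both for static gene expression at time of diagnosis as well as evolution of gene expression in response to chemotherapy".
- Section 10.0: the two specimens are used "to see the changes in gene expression, categorized based upon correlation to nodal status".

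The method follows directly in Section 10.0: "A paired t-test and multiple comparisons will be performed". No other section names a test for this objective. Section 10.0 also fixes the planned group sizes: "We designed this pilot study on 30 patients who receive chemoradiation and on 10 patients who receive chemotherapy alone". It expects at most 10% of patients to lack a paired profile.

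**The concern.** The question set is between groups: is the change in expression different in patients who remain node-positive? The test named is within patients. Nodal status takes one value per patient, so it cannot be the paired factor.

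That leaves the analyst two ways to use the paired test. One is to run it separately in each nodal group and compare which genes reach significance. The other is to run it on all patients together, in which case nodal status does not enter. With groups of 30 and 10, the first mostly compares the power of the two groups. Section 9.0 foresees developing the findings into a predictor of chemotherapy response, so genes wrongly labelled as specific to one nodal group could be the leads taken forward.

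The reference to multiple comparisons does not close the gap. If it means the nodal comparison, no statistic is given; if it means adjustment across the panel, no procedure is given. A lesser point is that a paired test cannot address expression at diagnosis, which Section 9.0 includes but Sections 2.2 and 2.4 do not.

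**Working it through.** **Inputs.** From Section 10.0: 30 node-positive and 10 node-negative patients, and at most 10% without a paired profile. If that loss were the full 10% and even across groups (an assumption), 30 × 0.9 = 27 and 10 × 0.9 = 9 would remain. The documents give no expression SD, effect size, significance level or panel size for this analysis. Assumed here: two-sided 5%, and within-patient changes that are normal with SD 1, so effects are in SDs of the change.

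**The plan's own figures.** None is given for the correlative analysis. The only precision figures are the Wilson half-widths for the primary endpoint, z·√(p(1−p)/n + z²/4n²)/(1 + z²/n). At p = 0.5 these are 16.8% (n = 30) and 26.3% (n = 10), in line with the stated limits of 17% and 26.5%. The planned group sizes are therefore not in dispute.

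**What each test tests.** Let μ₊ and μ₋ be the mean changes in node-positive and node-negative patients.

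- Paired, within group: μ₊ = 0 and μ₋ = 0, tested separately.
- Paired, pooled: 0.75μ₊ + 0.25μ₋ = 0.
- Needed for the objective: μ₊ − μ₋ = 0.

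**Within-group tests when there is no nodal link.** Power comes from the noncentral t with noncentrality d√n. At d = 0.5 in both groups, power is 0.754 (n = 30) and 0.293 (n = 10). The chance that the two results disagree is

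0.754 × (1 − 0.293) + 0.293 × (1 − 0.754) = 0.533 + 0.072 = 0.605.

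The 0.533 is the share significant in node-positive patients only. Across values of d:

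| Equal change d (SD) | 0 | 0.2 | 0.3 | 0.5 | 0.8 | 1.0 | 1.2 |
|---|---|---|---|---|---|---|---|
| Disagree, 30 and 10 | 9.5% | 24.0% | 39.5% | 60.5% | 38.6% | 19.7% | 8.0% |
| Disagree, 27 and 9 | 9.5% | 22.5% | 36.8% | 59.8% | 44.3% | 25.3% | 11.8% |

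**All three approaches compared** (simulation, 200,000 runs, 30 and 10). The first row has no nodal link; all others have a true difference of 1 SD.

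| μ₊ / μ₋ | Pooled mean | Pooled paired rejects | Within-group results disagree | Welch on change rejects |
|---|---|---|---|---|
| 0.5 / 0.5 | 0.50 | 86.8% | 60.5% | 5.2% |
| 0.25 / −0.75 | 0 | 3.3% | 52.9% | 72.6% |
| 0 / 1 | 0.25 | 27.7% | 77.3% | 72.5% |
| 0.2 / 1.2 | 0.45 | 73.7% | 76.5% | 72.6% |
| 0.8 / −0.2 | 0.55 | 89.4% | 90.3% | 72.7% |
| 1 / 0 | 0.75 | 99.3% | 94.9% | 72.5% |
| 1 / 2 | 1.25 | 100.0% | 0.1% | 72.7% |

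The pooled paired test follows the pooled mean, not the difference. Within-group disagreement ranges from 0.1% to 95% for the same nodal difference.

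**Why Welch rather than equal variances.** A time-by-nodal-status interaction with a common variance is the same as the equal-variance t-test on the change. If the node-negative SD is 1.5 times the node-positive SD, the true variance of the difference is 1/30 + 2.25/10 = 0.258. The equal-variance formula expects (29 × 1 + 9 × 2.25)/38 × (1/30 + 1/10) = 0.173, which is too small. Simulated type I error is 10.7%. In the reverse case it is 1.8%. Welch gives 5.1% and 5.0%.

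**Sensitivity of the right test.** One unadjusted Welch test has 80% power at 1.09 SD (30 and 10) or 1.16 SD (27 and 9). Suppose Benjamini-Hochberg at 5% across 20 to 100 independent genes, with 50% down to 5% of them truly linked. Then 80% average power over the linked genes needs about 1.3 to 1.7 SD (30 and 10) or 1.35 to 1.9 SD (27 and 9).

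**The case against.** The strongest reply is that the plan is incomplete rather than wrong. Section 4.3 states the node-positive versus node-negative comparison, and Section 10.0 mentions nodal status just before the test. On that reading the paired test covers the pre-to-post change and the multiple comparisons are loose wording for the nodal contrast. Nor do the documents say that a nodal link will be declared when one group is significant and the other is not. The analysis is exploratory and drives no decision in this trial.

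Parts of this stand. The intended contrast is clear, the paired test is valid for overall change, and the stakes are modest. The disagreement figures matter only if within-group results are compared, and they rest on assumed effects. The 27 and 9 case is a limit, since inclusion criteria 5 and 6 in Section 5.1 require both specimens. Welch is one reasonable choice among several, and strict false-discovery control is a matter of preference with about 10 node-negative patients.

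The core is untouched. Even on the kindest reading, no between-group statistic is named anywhere, and the one test that is named has a different null hypothesis. That needs no assumed effect size.

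**Conclusion.** The concern holds. The stated test cannot answer the correlative objective, either pooled or within nodal groups, and nothing else in the documents supplies the missing comparison. How far it could mislead depends on assumptions. With equal changes of 0.2 to 0.5 SD in both groups and 30 and 10 patients, within-group significance would disagree in 24% to 60% of genes that have no nodal link. A pooled test could detect a 1 SD nodal difference almost always or almost never, depending on the average change.

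The gap should be corrected before the expression data are analysed. It is confined to an exploratory secondary objective and leaves the primary feasibility endpoint, the sample size and patient care as they are.

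**What to change.** Replace the method sentence in Section 10.0 with text such as:

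> The paired t-test will describe the overall change in each gene after chemotherapy. For each gene, the within-patient change (surgical minus diagnostic specimen, on a scale fixed before analysis) will be compared between node-positive and node-negative patients by Welch two-sample t-test, with the difference and its 95% CI. The false discovery rate will be controlled at 5% across the panel (Benjamini-Hochberg).

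Another two-sample test would serve if fixed in advance. The false-discovery level is open to choice, but the plan should state one method.

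To cover the Section 9.0 aim on expression at diagnosis, add that diagnostic-biopsy expression will be compared between the same groups in the same way, as a separate exploratory family with its own false-discovery control. This addition can be separated from the main correction.

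Also state the sensitivity: about 1.1 SD for a single unadjusted test, and more after adjustment, with the assumptions listed.

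The cost is a few sentences and a few lines of code on the same data, with no added patients, samples or visits. There are two drawbacks. The plan would have to admit that only large nodal differences are detectable. If the SDs are in fact equal, Welch also gives up a little power against the equal-variance test (73% versus 76% at 1 SD).
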